**Table 1: Summary of outcome measures and assessment time points**

Outcome	Assessment time point
Total active motion	8 weeks
QuickDASH	6 and 8 weeks
Extensor lag	8 weeks
Grip strength	8 weeks
Adhesion-related events	Up to 8 weeks
Complications	Intraoperative to 8 weeks
Return to work	Up to 8 weeks
Patient satisfaction	8 weeks

## **Data Collection and Management**

Clinical and functional data were collected prospectively using standardized case report forms at each follow-up visit. Data were anonymized using unique study identifiers and entered into a secure, password-protected electronic database with restricted access. Data validation checks were performed to minimize entry errors, and all study records were maintained in accordance with institutional and regulatory requirements.

## **Sample Size Calculation**

The sample size was calculated to detect a clinically meaningful difference in total active motion between the two groups at eight weeks. Assuming a moderate-to-large effect size of 0.75, a two-sided alpha level of 0.05, and a power of 80%, a minimum of 28 patients per group was required. To account for potential attrition and incomplete follow-up, the sample size was increased to 30 patients per group, resulting in a total sample size of 60 participants.

## **Statistical Analysis Plan**

All analyses were performed using an intention-to-treat approach, including all randomized participants in their allocated groups. A per-protocol analysis will be conducted as a secondary exploratory analysis.

Continuous variables were expressed as mean  $\pm$  standard deviation or median with interquartile range, depending on distribution. Categorical variables will be expressed as frequencies and percentages. Between-group comparisons of the primary outcome were performed using an independent samples t-test for normally distributed data or the Mann–Whitney U test for non-normally distributed data. Proportions of patients achieving good or excellent functional outcomes based on established extensor tendon scoring systems were compared using chi-square or Fisher’s exact tests.

Secondary outcomes were analysed using appropriate parametric or non-parametric tests. Repeated-measures analysis of variance or mixed-effects models was used to evaluate changes in functional scores over time. Effect sizes were reported using Cohen’s d for continuous outcomes and relative risk or odds ratios for categorical outcomes, with corresponding 95% confidence intervals. Two-sided p-values less than 0.05 was considered statistically significant.

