### **Outcome Measures**

The primary outcome measure was total active motion of the involved digit or digits at eight weeks postoperatively. Total active motion was calculated as the sum of active flexion at the metacarpophalangeal, proximal interphalangeal, and distal interphalangeal joints minus extension deficits. Results were expressed in degrees and as a percentage of the contralateral uninvolved digit or standardized normative values.

Secondary outcomes included QuickDASH scores at six and eight weeks, extensor lag at individual joints measured in degrees at eight weeks, grip strength measured using a calibrated Jamar dynamometer at eight weeks, incidence of adhesion-related events including failure to achieve functional motion thresholds or need for tenolysis, complication rates, time to return to work or activities of daily living, and patient satisfaction scores (Table 1).

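### The primary analysis is not fixed: test and outcome scale are left open, no covariate is used, and no difference in degrees with a confidence interval is planned

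*Combined protocol and SAP*

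**What the plan says.** Four elements of the primary analysis are spread over three sections of the combined protocol and SAP.

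- **Test** (Statistical Analysis Plan): groups are compared "using an independent samples t-test for normally distributed data or the Mann–Whitney U test for non-normally distributed data". No normality test, cut-off or variable to be checked is given, and no covariate is named.
- **Scale** (Outcome Measures): "Results were expressed in degrees and as a percentage of the contralateral uninvolved digit or standardized normative values". No section says which scale carries the primary test, or when the contralateral digit gives way to a norm.
- **Effect measure** (Statistical Analysis Plan): "Effect sizes were reported using Cohen’s d for continuous outcomes", with 95% confidence intervals. Group summaries are mean and SD, or median and interquartile range, depending on distribution.
- **Target** (Sample Size Calculation): the trial is sized for "a clinically meaningful difference in total active motion between the two groups at eight weeks", but the only figure is a standardised one: "Assuming a moderate-to-large effect size of 0.75". No SD and no difference in degrees are stated.

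There are two centres and three zones, and a patient may have several injured digits. The randomisation section mentions blocks of four and six but no stratification.

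**The concern.** A primary analysis should be determined before the data are seen. Here two choices stay open. The t-test concerns means and Mann–Whitney concerns ranks, so the question being answered depends on the data. With no primary scale named, an analyst could report degrees or percentage, whichever looks better, and no text would rule it out.

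Two further losses follow. Centre, zone, number of involved digits and contralateral motion may predict TAM, but the planned test ignores them. And a standardised effect cannot show whether a clinically meaningful number of degrees was gained. It also does not correspond to a Mann–Whitney result, should that test be used.

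**Working it through.** **Inputs from the Sample Size Calculation.** d = 0.75; "a two-sided alpha level of 0.05"; power 80%; "a minimum of 28 patients per group was required"; and "the sample size was increased to 30 patients per group, resulting in a total sample size of 60 participants". The documents give no SD of TAM, no contralateral SD and no R² for any covariate. Those below are assumptions, shown as ranges.

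**1. The plan's own figure.** n per group = 2(1.960 + 0.842)² / 0.75² = 15.70 / 0.5625 = 27.9, so 28. This reproduces the plan. The noncentral-t calculation gives 28.9, so 29. Unadjusted t-test power is 78.7% at 28 per group and 81.5% at 30.

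**2. Choosing the test by a rule.** Null trials with 30 per group were simulated 20,000 times. Shapiro–Wilk was applied in each arm; if either p-value was below 0.05, Mann–Whitney was used, otherwise the t-test.

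| Distribution | Sent to Mann–Whitney | Type I error, rule followed | Type I error, smaller p taken |
|---|---|---|---|
| Normal | 10% | 4.9% | 5.6% |
| Bounded, left-skewed | 78% | 5.3% | 6.2% |
| Moderate left skew | 70% | 5.5% | 6.5% |
| Strong skew | 99.9% | 4.5% | 6.4% |
| t with 3 df | 71% | 5.0% | 6.4% |

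The simulation standard error is √(0.05 × 0.95 / 20,000) = 0.15 points. A rule-bound switch therefore stays within about half a point of nominal.

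**3. Open choice of scale.** Assume contralateral TAM has mean 260 and SD s, and injured TAM is a fraction of it (mean 0.81, SD 25/260 = 0.096). Type I error if success on either scale counts (t-test, 30 per group, 40,000 runs):

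| s (degrees) | Correlation of scales | Type I error |
|---|---|---|
| 5 | 0.987 | 5.7% |
| 10 | 0.951 | 6.5% |
| 15 | 0.898 | 7.1% |
| 20 | 0.838 | 7.6% |

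A second model, injured TAM = 0.8 × contralateral + N(0, 28), gives about 5.6% to 7.3% over the same s. The combined range is 5.6% to 7.6%. Free choice of both scale and test gives about 6.7% to 8.9%. For comparison, two independent tests would give 1 − 0.95² = 9.75%.

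**4. Power with adjustment.** For k covariate terms, the noncentrality is d/√(1 − R²) × √(n/2), with 2n − 2 − k degrees of freedom. At n = 30 and R² = 0 this is 0.75 × 3.873 = 2.90; at R² = 0.20 it is 2.90 / 0.894 = 3.25.

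| R² (assumed) | 0 | 0.05 | 0.10 | 0.20 | 0.30 |
|---|---|---|---|---|---|
| Power, 30 per group | 81.4% | 83.3% | 85.3% | 89.1% | 92.7% |

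These use k = 3; four or five terms change them by about 0.1 points. The R² from contralateral TAM alone depends on s. Under the second model it is (0.8s)² / [(0.8s)² + 28²]: 16/800 = 0.02 at s = 5, 64/848 = 0.08 at s = 10, and 256/1,040 = 0.25 at s = 20.

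**5. What d says in degrees.** d = 0.75 is 7.5 degrees at SD 10, 15 at SD 20, 22.5 at SD 30 and 30 at SD 40. With 30 per group, an observed d of 0.75 has SE √(2/30 + 0.75²/120) = 0.267 and a 95% CI of 0.75 ± 0.52, about 0.23 to 1.27. Without an SD this cannot be read clinically.

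**The case against.** Three stronger readings are tempting, and the documents do not support them.

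*Both scales are tested, so type I error is 7.5% or 8.9%.* A reader might infer this, but the plan says only that results are expressed both ways and describes one comparison of the primary outcome. The flaw is an unnamed scale. Those figures describe a best-of-several analysis at the top of an assumed SD range.

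*Letting the distribution choose the test breaks the error rate.* Step 2 shows that it does not if a rule is followed. The analyst is also blinded to allocation, which limits steering towards one arm, though not selection of the smaller p-value.

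*Adjustment is worth 25% to 43% more patients.* That is 1/(1 − 0.20) to 1/(1 − 0.30), so it assumes the R² it needs. No section supports strong predictors, and no pre-operative TAM of the injured digit is listed. Contralateral TAM is not assured for everyone either, since norms may replace it. Under moderate skew with no covariates, Mann–Whitney had 85% simulated power against 81% for the t-test.

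It is also fair that group means and SDs in degrees would let a reader derive a difference when the t-test is used. That fails when medians are reported, and a difference with its interval is nowhere planned.

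These arguments reduce the size of the problem. They do not supply a criterion, a primary scale, a covariate or an effect in degrees.

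**Conclusion.** The point stands in this form: test and scale are open, the comparison is unadjusted, and the planned effect measure is not in clinical units. The error-rate consequence is modest and conditional. It is near nominal for rule-bound test choice, about 5.6% to 7.6% if either scale may count, and about 6.7% to 8.9% if scale and test are both free. The last two rest on assumed contralateral SDs of 5 to 20 degrees and on success being claimed from whichever analysis works, which the plan does not state but does not exclude.

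The case for adjustment is that it costs about 0.1 points of power if the covariates are useless and may add about 2 to 11 points for R² between 0.05 and 0.30. A gain is possible but not demonstrated. None of this invalidates the trial, but it concerns the primary result and should be settled before unblinding.

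**What to change.** Amend the SAP as follows.

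1. **Scale.** Name TAM in degrees as the primary scale, one value per patient, for example the mean over involved digits.
2. **Model.** Fit one pre-specified linear model of TAM on treatment, centre, most proximal zone involved, number of involved digits, and contralateral TAM averaged over the same digits. Where the contralateral digit cannot be measured, use a normative value from a source named in advance, and report how often this happened. Using the most proximal zone classifies patients injured in more than one zone.
3. **Report.** Give the adjusted mean difference in degrees with a 95% CI, using model-based standard errors or HC3 with t critical values. The type matters: HC0 with normal critical values gave 6.7% type I error in a simulation with 60 patients. Cohen's d can remain as a supplement.
4. **Sensitivity analyses.** Keep percentage TAM and Mann–Whitney here.
5. **Interpretation.** State the difference in degrees regarded as clinically meaningful, and the SD that makes it d = 0.75.

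The cost is wording, no extra patients, and 4 to 5 degrees of freedom: centre 1, zone 1 or 2, digits 1, contralateral TAM 1. Number of involved digits and contralateral TAM must be recorded for every patient, which the documents do not now guarantee. If TAM is markedly skewed and the covariates are weak, the linear model may lose some power against Mann–Whitney.

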### **Randomization, Allocation Concealment, and Blinding**

Eligible patients were randomized in a 1:1 ratio to the experimental or control group using a computer-generated randomization sequence with variable block sizes of four and six. The randomization sequence was prepared by an independent statistician not involved in patient care.

Allocation concealment was ensured using sequentially numbered, opaque, sealed envelopes, which were opened in the operating room after confirmation of eligibility and completion of tendon exposure. Due to the nature of the intervention, blinding of the operating surgeon and patient was not feasible. However, outcome assessors, including hand therapists performing functional measurements and clinicians evaluating outcomes, were blinded to group allocation. The data analyst was also blinded to treatment assignment.

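### The graded extensor tendon score is tested only as good-or-excellent versus the rest, which discards the ordering within the merged grades and costs power on a supporting analysis

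*Combined protocol and SAP*

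**What the plan says.** The Statistical Analysis Plan states: "Proportions of patients achieving good or excellent functional outcomes based on established extensor tendon scoring systems were compared using chi-square or Fisher’s exact tests". It does not name the scoring systems, their grades or their cut-offs.

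Nothing else in the plan supplies a test on the full grades. One general sentence leaves secondary outcomes to whichever parametric or non-parametric test suits them, but the graded score has its own sentence, and that sentence fixes a two-category comparison. The repeated-measures sentence concerns scores followed over time, and Table 1 schedules only QuickDASH at more than one visit.

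The primary outcome is not cut. Under Outcome Measures, "The primary outcome measure was total active motion of the involved digit or digits at eight weeks postoperatively", and the plan tests it on its full scale by t-test or Mann–Whitney U. Neither Outcome Measures nor Table 1 lists an extensor tendon score.

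The Sample Size Calculation is written for total active motion only. It gives an effect size of 0.75 with "a two-sided alpha level of 0.05" and 80% power, concludes that "a minimum of 28 patients per group was required", and adds that "the sample size was increased to 30 patients per group, resulting in a total sample size of 60 participants".

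**The concern.** Good and excellent are separate ordered grades with at least one grade below them. Collapsing them to two categories keeps only movement across a single boundary. A patient who ends excellent rather than good contributes nothing, and neither does one who ends fair rather than poor, if those are the lower grades. The documents give no clinical or regulatory reason for testing at that boundary alone.

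With 30 patients per arm there is little information to spare. A non-significant grade comparison beside a clear result on total active motion could be read as an absence of functional benefit when it partly reflects the cut. The plan already accepts a rank test for the primary outcome, so an analysis that uses the ordering needs no unfamiliar method.

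**Working it through.** **1. The plan's own figure.** Normal approximation: n per group = 2(1.960 + 0.842)² / 0.75² = 27.9, rounded up to 28. This reproduces the stated minimum. The exact t-test calculation gives 28.9, that is 29. At d = 0.75 the t-test has 78.7% power with 28 per group and 81.5% with 30. The sample size is not in dispute.

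**2. Inputs for the graded score.** From the documents: 30 per group, 1:1 allocation, two-sided 0.05, and 0.75 SD (stated for total active motion, borrowed here). Assumed, because the documents are silent:
- four grades (poor, fair, good, excellent) cut from a normal latent scale;
- a control good-or-excellent rate of 30–80%;
- the excellent share of the top two grades, and the poor share of the bottom two, each set at 30%, 50% or 70%.

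**3. Model.** If the control arm has cumulative probability c at a grade boundary, the treated arm has Φ(Φ⁻¹(c) − d).

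**4. One case by hand.** Put 25% of controls in each grade and take d = 0.75.
- Treated good or excellent: Φ(0.75) = 0.773, against 0.500.
- Treated excellent: 1 − Φ(0.674 − 0.75) = 0.53, against 0.25. The 2×2 table cannot see the movement from good to excellent.
- Chi-square power: the pooled proportion is 0.637, the null SE is √(2 × 0.637 × 0.363/30) = 0.124, and the alternative SE is √((0.250 + 0.175)/30) = 0.119. Then (0.273 − 1.96 × 0.124)/0.119 ≈ 0.25, and Φ(0.25) ≈ 0.60. Exact enumeration of all 2×2 tables gives 59.9%.
- Tie-corrected Wilcoxon-Mann-Whitney (WMW) test on all four grades, by simulation: 74%.
- Loss from merging: 74 − 60 = 14 points.

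**5. Range at d = 0.75, 30 per group.** Chi-square (uncorrected) and Fisher power are exact. WMW power is simulated, and its range covers the nine grade mixes.

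| Control → treated, good or excellent | Chi-square | Fisher | WMW, all grades | Loss, chi-square (points) |
|---|---|---|---|---|
| 30% → 59% | 63% | 53% | 73–76% | 10–13 |
| 40% → 69% | 63% | 53% | 72–76% | 9–13 |
| 50% → 77% | 60% | 50% | 71–76% | 11–16 |
| 60% → 84% | 56% | 46% | 68–75% | 12–18 |
| 70% → 90% | 49% | 37% | 65–73% | 16–24 |
| 80% → 94% | 41% | 22% | 61–71% | 20–30 |

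If the plan means a switch to Fisher when an expected count falls below 5, power at the 80% control rate is about 25%.

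**6. Sensitivity.**
- At d = 0.5 on the same grid the chi-square loss is about 6 to 16 points.
- With a logistic latent scale at 0.75 and control rates of 30–70% it is 6 to 28 points.
- The direction did not reverse for any non-zero effect tried (0.5, 0.75, 1.0).

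**7. Error rates under no effect.** WMW 4.7–5.3%, chi-square 4.9–5.2%, Fisher 2.2–2.7%. The WMW gain is not bought with type I error. Fisher's extra shortfall on the same 2×2 table (60 − 50 = 10 points at a 50% control rate) comes from its conservatism, not from merging grades.

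**The case against.** The strongest reply is about weight. The score is absent from Outcome Measures and Table 1. Functional benefit rests on total active motion, QuickDASH, extensor lag and grip strength, and no cut is planned for those measurements. A responder proportion is a legitimate clinical summary. The plan also promises relative risks or odds ratios with 95% confidence intervals, so a non-significant result would be shown with its imprecision. If the grade is derived from total active motion, the primary test already uses the uncut information. All of this stands and keeps the point modest.

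A reader might infer that the planned test would miss the effect the trial assumes in some 37–59% of cases (100 − 63 and 100 − 41). The documents do not support that wording: they assume 0.75 for total active motion and nothing for any score. A reader might also take one narrow band of power loss as fixed. It is not, because it moves with the effect, the grade mix and the control rate, none of which is given for this score.

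The reply does not remove the central fact that no sentence names a test on all the grades. The confidence interval around the good-or-excellent contrast shows the imprecision of the cut comparison; it does not recover the ordering.

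**Conclusion.** The point holds as a modest efficiency finding on a supporting analysis. Testing only good-or-excellent versus the rest discards usable ordering. Under a four-grade normal latent model with 30 per arm and a control rate of 30–80%, chi-square loses roughly 9 to 30 points of power against a test on all grades if the effect is 0.75 SD, and about 6 to 16 points if it is 0.5 SD. The direction is robust. The size rests on assumptions the documents do not supply and should always be quoted with them.

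It would be too strong to read this as a weakness in the trial's main functional result: total active motion is analysed on its full scale, and its sample size calculation reproduces. Nor should the whole shortfall of Fisher's exact test be put down to the cut.

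**What to change.** In the Statistical Analysis Plan:

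1. Name the single scoring system used, with its grades and cut-offs. The present plural leaves the test unspecified.
2. Make the between-group test a tie-corrected Wilcoxon-Mann-Whitney test on all its ordered grades.
3. Report the count and percentage in each grade by arm.
4. Keep the good-or-excellent proportion, with its relative risk or odds ratio and 95% CI, as a supporting summary.
5. Optionally add a proportional-odds common odds ratio with 95% CI, if the grades are not too sparse.

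The cost is a few sentences of wording; no extra patients, visits or measurements are needed. If data have already been collected, the change should be dated and disclosed. The small downside is that a rank test is less directly readable than a percentage, which is still reported.

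### At 30 per arm, Fisher's exact test is very conservative for sparse proportions; Boschloo's exact test is a cheap gain, and the plan lacks a rule for choosing the test

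*Combined protocol and SAP*

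**What the plan says.** The Statistical Analysis Plan assigns a test for proportions to one endpoint only, the share of patients rated good or excellent on extensor tendon scores. These are "compared using chi-square or Fisher’s exact tests". It does not say when each test applies.

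Outcome Measures also lists complications and the "incidence of adhesion-related events including failure to achieve functional motion thresholds or need for tenolysis". Both are naturally compared as proportions, but the plan covers secondary outcomes only by a general reference to suitable parametric or non-parametric methods. The threshold is common to all analyses: "Two-sided p-values less than 0.05 was considered statistically significant".

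The trial is sized on total active motion alone, and "the sample size was increased to 30 patients per group, resulting in a total sample size of 60 participants". No event rate is assumed for any binary outcome. The only rate in the document is in the Introduction, where adhesions are put at up to 30-40% as background.

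**The concern.** Chi-square and Fisher's test are the only methods named for proportions, so an analyst would probably use them for complications and adhesion events too, and turn to Fisher when counts are small. Fisher's test conditions on the total number of events, which this design does not fix. With few events the attainable p-values are coarse, and the true error rate falls far below the nominal 5%.

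Boschloo's test orders the tables by Fisher's p-value but calibrates the cut-off with only the arm sizes fixed. It rejects whenever Fisher's test rejects, so it cannot be less powerful. At stake is some power for uncommon outcomes, harms included, that costs no patients to recover. Separately, leaving the choice of test open until the data are seen is a gap in prespecification.

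**Working it through.** **Inputs from the document.** Allocation: "Eligible patients were randomized in a 1:1 ratio". Planned size: 30 per arm. Threshold: two-sided 0.05.

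**The plan's own figure.** The inputs are "Assuming a moderate-to-large effect size of 0.75" and "a two-sided alpha level of 0.05, and a power of 80" percent. The normal approximation gives n = 2 × (1.960 + 0.842)² / 0.75² = 27.9, so 28 per arm, which agrees with "a minimum of 28 patients per group was required". (The t-based solution is 28.9, so 29; this is immaterial here.) Going from 28 to 30 allows 2/30 = 6.7% attrition. None of this concerns a binary outcome.

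**Assumptions.** All event rates below are assumed. So is the switching rule: Fisher if any expected count is below 5, otherwise Pearson chi-square. With equal arms, the expected number of events per arm is half the total, so the Fisher branch applies when total events (or non-events) are fewer than 10 of 60, an overall rate below about 17%.

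**Method.** Enumerate all 31 × 31 tables. For rates p₁ and p₂, the rejection probability is the sum, over rejected tables (a, b), of Bin(a; 30, p₁) × Bin(b; 30, p₂). Setting p₁ = p₂ gives the true error rate.

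**Step 1: true error rate (%).**

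| Common event rate | Fisher alone | Boschloo alone | Mixed rule with Fisher |
|---|---|---|---|
| 5% | 0.15 | 0.71 | 0.15 |
| 10% | 0.94 | 2.33 | 1.22 |
| 20% | 2.22 | 3.14 | 4.20 |
| 30% | 2.61 | 3.65 | 4.86 |
| 50% | 2.74 | 4.67 | 5.19 |

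Fisher's size is about 1.9% at a rate of 1/6, the edge of its branch. Its 2.74% maximum is at a 50% rate, where the assumed rule uses chi-square.

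**Step 2: what Boschloo's test changes.** The largest Fisher p-value that can serve as a cut-off while keeping maximum size at or below 5% is 0.0692 (maximum size 4.69%); the next attainable value, 0.0698, gives 5.19%. Within the Fisher branch this adds only 0 v 5 and 1 v 7 events and their mirror images. For 0/30 v 5/30:

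- Fisher: p = 2 × C(30,5)/C(60,5) = 2 × 142,506/5,461,512 = 0.052.
- Boschloo: p = 0.027, the maximum over the common rate of the probability of a table with Fisher p no larger than 0.052.

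**Step 3: power (%), replacing only the Fisher branch.** Gains are computed before rounding.

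| Assumed rates | With Fisher | With Boschloo | Gain (points) |
|---|---|---|---|
| 2% v 15% | 18.8 | 31.7 | 12.9 |
| 3% v 20% | 36.2 | 48.8 | 12.6 |
| 5% v 20% | 27.5 | 36.4 | 8.9 |
| 5% v 25% | 49.2 | 57.1 | 7.9 |
| 5% v 30% | 69.4 | 74.5 | 5.1 |
| 10% v 30% | 46.8 | 48.7 | 1.9 |
| 15% v 30% | 27.2 | 27.8 | 0.5 |
| 10% v 40% | 79.1 | 79.4 | 0.4 |
| 20% v 40% | 39.2 | 39.2 | 0.0 |

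Mirror pairs give the same figures: 95% v 75% good or excellent equals 5% v 25%.

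Hand check at 5% v 25%. For 0 v 5: 0.95³⁰ × C(30,5) × 0.25⁵ × 0.75²⁵ = 0.2146 × 0.1047 = 0.0225. For 1 v 7: 30 × 0.05 × 0.95²⁹ × C(30,7) × 0.25⁷ × 0.75²³ = 0.3389 × 0.1662 = 0.0563. The sum is 0.0788, the 7.9 points in the table; the reversed tables add almost nothing.

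**Step 4: attrition.** At 28 per arm the same replacement gives 43.4 to 52.4 (5% v 25%), 31.0 to 44.0 (3% v 20%) and 15.4 to 27.6 (2% v 15%).

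**The case against.** The strongest case against is that this is a matter of preference. Chi-square with Fisher as fallback is conventional, and Fisher's conservatism does not inflate false positives. The outcomes are not primary, and the plan also reports relative risks or odds ratios with confidence intervals. The only rate in the document, adhesions at up to 30-40%, is not sparse. With 40% in one arm, reductions to 20% or 10% gain 0.0 and 0.4 points. The good/excellent endpoint at 80% v 60% gains nothing. The whole benefit comes from two table patterns and their mirrors.

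Most of that stands, and it limits the size of the point. It does not remove it. Complications may well be rare, and so may adhesion events in one arm: 30% v 5% still gains 5.1 points. The added patterns are realistic results in 60 patients. Chi-square, which the plan already accepts, does not condition on the event total either, so Boschloo's test brings in no new principle.

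Four stronger readings are tempting, and the documents or the arithmetic do not support them:

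- *The plan sends sparse outcomes to Fisher's test.* A reader might infer this, but the clause covers one endpoint, states no switching rule, and leaves adhesion events and complications without a named test.
- *The plan's error rate is at most 2.7%.* That is Fisher applied to every table. Under the assumed rule the rate is 4.2% at a 20% event rate and 4.9% at 30%.
- *The change keeps the error rate within 5%.* The mixed rule reaches 5.2% with either exact test, because of its chi-square branch.
- *Differences would be missed only because of the test.* With Boschloo's test, power is still 32% to 57% in four of the five sparse pairs. At 5% v 10% it goes from 2.1% to 4.9%. Sample size is the main limit.

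**Conclusion.** The point holds as a low-severity improvement. The firm documentary gap is that the plan has no rule for choosing between chi-square and Fisher's test, and names no test for adhesion events or complications. The efficiency gain is conditional on Fisher being used when an expected count is below 5. It is then about 5 to 13 points of power where one arm is at 2-5% and the other at 15-30% (or the mirror), and 0 to 2 points in the pairs tested with 30-40% against 10-20%. Every event rate is an assumption. The primary analysis and the sample size are unaffected, and no stated figure is wrong.

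**What to change.** In the Statistical Analysis Plan, replace the clause on tests for proportions with wording such as: *All binary outcomes, including good/excellent result, adhesion-related events and complications, will be compared with Boschloo's unconditional exact test (two-sided) when any expected count is below 5, and with the chi-square test otherwise.*

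This is one sentence, needs no extra patients, and uses a test available in standard software. It can only add power relative to Fisher in that branch, and leaves the rule's maximum size at 5.2%. If a strict 5% ceiling is wanted, Boschloo's test can be used throughout (maximum 4.69%). That costs power where chi-square would now apply: about 4.2 points at 10% v 30% and 6.0 at 15% v 40%, compared with the assumed chi-square/Fisher rule. The main downside is that readers know Boschloo's test less well. If the sponsor prefers to keep Fisher's test, stating the switching rule and the test for each binary outcome still closes the documentary gap.

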### **Postoperative Splinting and Rehabilitation Protocol**

All patients were placed in a standardized dorsal protective splint with the wrist in extension and the metacarpophalangeal joints positioned according to the involved zone and institutional extensor tendon protocol. Postoperative rehabilitation was standardized across both groups and supervised by certified hand therapists.

Initial immobilization was maintained for five to seven days. Controlled early active or early controlled motion protocols were then initiated based on institutional standards for zones VI–VIII, progressing to increased range of motion exercises by three to four weeks and gradual strengthening by six weeks. No additional anti-adhesion agents or topical products targeting tendon healing were permitted during the study period.

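### Time to return to work stops at 8 weeks, but the plan names no time-to-event method and no rule for patients not back by then or lost earlier

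*Combined protocol and SAP*

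**What the plan says.** The Outcome Measures section lists, among the secondary outcomes, "time to return to work or activities of daily living". Table 1 carries one matching row, "Return to work", assessed up to 8 weeks. It has no row for daily activities.

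The Statistical Analysis Plan has one sentence that covers the analysis of this outcome: "Secondary outcomes were analysed using appropriate parametric or non-parametric tests". Continuous variables are summarised as mean with "standard deviation or median with interquartile range, depending on distribution". Effect sizes are Cohen's "d for continuous outcomes and relative risk or odds ratios for categorical outcomes". The section also commits all analyses to intention to treat, with every randomised patient kept in the assigned arm.

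Kaplan–Meier, log-rank, Cox and restricted mean methods do not appear. There is no rule for a patient who has not returned at 8 weeks, or for one lost before then.

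**The concern.** A patient still off work at 8 weeks has no return time, only the knowledge that it exceeds 8 weeks. Non-return by then is plausible: the rehabilitation section places "gradual strengthening by six weeks", which leaves two weeks to the end of observation. Loss before week 8 is also foreseen, because the Sample Size Calculation adds patients for attrition and incomplete follow-up.

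None of the plan's stated summaries can represent such a patient. A mean, a median with quartiles or a Cohen's d needs a number for everyone, and relative risk or odds ratio reduces the outcome to yes or no. The easiest course for an analyst following these summaries is to use the recorded return times. That drops the non-returners, a group defined after randomisation by the outcome itself, and cuts both arms off at 8 weeks. A wrap that speeds return would then show little or no benefit on this outcome.

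The definition is open as well. Work and daily activities are different events and may occur at different times, and the plan does not say which one ends the interval.

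**Working it through.** **The plan's own figure.** The only sample size is for the primary outcome. With d = 0.75, two-sided alpha 0.05 and 80% power, n = 2(1.960 + 0.842)²/0.75² = 27.9, so 28 per arm, as stated. Nothing is given for return to work, so the check below takes only the planned 30 per arm, the 8-week limit and alpha 0.05 from the documents. The return-time distributions are assumptions.

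**Step 1: how many are censored.** For a Weibull time with median m and shape k, the proportion not back at 8 weeks is S(8) = 0.5^((8/m)^k).

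| Median (weeks) | Shape 2 | Shape 3 |
|---|---|---|
| 9 | 0.58 | 0.61 |
| 7 | 0.40 | 0.36 |
| 6 | 0.29 | 0.19 |
| 5 | 0.17 | 0.06 |

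**Step 2: what each mean estimates, medians 9 and 7.** The mean restricted to 8 weeks is R = ∫₀⁸ S(t)dt. The mean among returners is (R − 8·S(8))/(1 − S(8)).

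- Shape 2: R = 6.75 and 6.12, a difference of 0.63 weeks. Returner means are (6.751 − 8 × 0.578)/0.422 = 5.04 and (6.122 − 8 × 0.404)/0.596 = 4.85, a difference of 0.19 weeks.
- Shape 3: R = 7.15 and 6.42, a difference of 0.73 weeks. Returner means are 5.79 and 5.55, a difference of 0.24 weeks.

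A two-week difference in medians becomes about a fifth to a quarter of a week among returners.

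**Step 3: power by simulation, 30 per arm, everyone followed to 8 weeks, shape 2 to 3.**

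| Medians | t-test, returners only | Log-rank |
|---|---|---|
| 9 vs 7 | 6–7% | 27–53% |
| 6 vs 5 | 7–19% | 23–51% |

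At 9 vs 7, a rank test with non-returners tied last has 25–52%. The returners-only mean points the wrong way, with the wrap looking slower, in 34–40% of trials.

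**Step 4: range over the unknown return rate.** Weibull shape 2.5, return-rate (hazard) ratio 2, 2,000 trials per column.

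| Controls back by 8 weeks | 30% | 50% | 70% | 90% |
|---|---|---|---|---|
| Log-rank | 40% | 56% | 68% | 72% |
| Rank test, non-returners tied last | 38% | 51% | 59% | 60% |
| t-test, non-returners set to 8 weeks | 29% | 42% | 57% | 65% |
| Fisher, returned by 8 weeks yes/no | 29% | 41% | 42% | 6% |
| t-test, returners only | 5% | 8% | 18% | 45% |

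Schoenfeld's formula confirms the log-rank row. With 50% of controls back, the treated proportion is 1 − 0.5² = 0.75 and the expected events are 30 × (0.50 + 0.75) = 37.5, so power = Φ(√37.5 × ln 2/2 − 1.96) = Φ(0.16) = 56%. In that column the mean difference is 1.98 weeks uncensored, 0.88 weeks restricted to 8 weeks, and 0.30 weeks among returners.

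**Step 5: no effect.** With a hazard ratio of 1, no method exceeded about 5–6% rejection.

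**The case against.** A reader might infer that the plan prescribes a t-test or Mann–Whitney test here and that such tests cannot deal with non-returners. The documents do not support either step. Those two tests are named for the primary outcome. For secondary outcomes the plan asks for appropriate tests, and log-rank is itself non-parametric, so the wording does not exclude it. Nor is a simple test always unsound. When every patient is followed to 8 weeks, a rank test with non-returners tied last is valid and loses little (51% against 56% with half the controls back). Setting non-returners to 8 weeks then estimates the restricted mean, which is also what the fix asks for.

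The lowest power figures apply only if non-returners are dropped. The plan does not say they are, and its intention-to-treat commitment speaks against it. Return rates are not given, and the rehabilitation timetable does not fix them. With 90% of controls back, the returners-only t-test reaches 45% against 72%, a smaller loss.

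All of this stands, and it limits the point to an open specification. It does not remove it. The plan adopts neither of the acceptable simple approaches, neither copes with loss before 8 weeks without a further rule, and the stated summaries and effect measures do not fit a censored time.

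**Conclusion.** The plan leaves the analysis of this outcome, and the counting of patients not back by 8 weeks or lost earlier, unspecified, and the summaries it does state cannot carry them. The choice matters: on the same assumed data, power runs from about 6–7% to 27–53% at medians of 9 and 7 weeks, and from about 7–19% to 23–51% at 6 and 5 weeks. The size rests on Weibull times, proportional hazards and complete follow-up to 8 weeks, none of which the documents can confirm. The harm is lost power and a shrunken estimate. There is no sign of excess false positives. The outcome is secondary, so the primary conclusion is not touched. The change should be made, but the trial does not depend on it.

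**What to change.** For this outcome, replace mean/SD and Cohen's d with wording such as: *Time to return to work is analysed in all randomised patients by Kaplan–Meier and log-rank, censored at 8 weeks or last contact, with the difference in restricted mean time to 8 weeks (95% CI).*

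State whether work or daily activities stops the clock, make Table 1 agree with Outcome Measures, and say how patients not working before injury are handled. Analyse daily activities as a separate time-to-event outcome only if its date is recorded. The Data Collection and Management section does not list the fields, so that cannot be assumed.

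Settle the wording before the analyst sees the arms. The cost is SAP text and slightly more analysis work, plus a date field if the case report form lacks one. The sample size and primary analysis stay as they are.
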